12.2.3. Feasibility Endpoint

Stopping guideline for feasibility

The feasibility of neoadjuvant durvalumab monotherapy (cohort 1) or durvalumab+tremelimumab (cohort 2) together with thoracic radiation prior to surgery will be based on the proportion of evaluable patients proceeding to surgery without extended treatment-related delays. A treatment-related delay will be considered "extended" if it is greater than 8 weeks following completion of thoracic radiation. For feasibility, drug-related toxicity of any grade, that in the judgment of the investigator or surgeon could adversely impact perioperative morbidity or mortality, should delay the planned operative date.

We would consider the experimental regimen is "infeasible" if the probability of not proceeding to surgery as planned is convincingly (more than 70%) more than .25, i.e., the probability of proceeding to surgery as planned is convincingly less than 75%. We assume about 10% of patients will have their surgery delayed and there is about 14% chance that the risk will be 25% or more. This corresponds to a Beta (0.1,0.9) prior distribution. Table 10.5 summarizes the continuous stopping rule for the 16 evaluable patients for each regimen. The feasibility stopping rule calls for the study to be paused for a review if the number of patients successfully proceeding to surgery is too low, starting from the 6th evaluable patient.

Table 10.5 Stopping Rule for Feasibility

# patients with delay in planned surgery	3	4	5	6
Out of total # evaluable patients	6-7	8-10	11-14	15-16

Table 10.6 summarizes the operating characteristics based on 5,000 simulations with 16 evaluable patients in terms of how frequent the study would stop based on the stopping rule under different hypothetical feasibility rates, as well as the average sample sizes.

Table 10.6 Operating characteristics of the stopping rule for feasibility

Underlying feasibility	0.65	0.7	0.75	0.8
% of time study stops	37.9%	13.9%	6.4%	2.1%

18-Nov-2020 Page **117** of **164**

Expected sample size	13.8	15.2	15.6	15.9

If the feasibility stopping boundary is reached, we will re-evaluate the clinical advantages of the treatment, pathological tumor response and prolonged RFS, against the risks and consider re-designing the regimen to allow more time between the last dose of immunotherapy and surgery to better manage potential side effects.

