The co-primary endpoints of this study are safety, tolerability and feasibility in cohort 1, followed by safety and feasibility in cohort 2. Safety will be monitored through the rate of all treated patients that develop adverse events (including serious and non-serious, as well as adverse events of special importance AESIs) and dose-limiting toxicities from commencement of durvalumab/RT or durvalumab/tremelimumab/RT until 30 days postoperatively or 100 days after the last dose of immunotherapy whichever is longer, or any pre-defined pulmonary DLTs that occur from the date of surgery until 30 days postoperatively. The DLT observation window will be defined as the time from the date of commencement of immunotherapy until 30 days post-surgery or 100 days after last immunotherapy dose, whichever is longer. Safety will be monitored continuously for all patients. A Bayesian safety monitoring rule will be used to evaluate the rate of adverse events of interest continuously, from the 3rd evaluable patient, and accrual will be suspended at any time if there is sufficient evidence of excessive toxicity. Specifically, the Bayesian toxicity monitoring rule suspends accrual anytime if the posterior probability of adverse event of interest being larger than 25%, is 70% or higher. The following table gives the corresponding stopping rule for the 16 evaluable patients:

#Patients with DLT	2	3	4	5	6
Out of total #patients treated	3-4	5-7	8-11	12-13	16

Feasibility will be monitored through the proportion of patients who undergo surgery within the planned surgical window: 6-8 weeks after completion of thoracic RT. We will use a probability-based decision rule to decide if the probability of successfully proceeding to surgery as planned is convincingly less than 75%. A Bayesian monitoring rule would apply and suspend the accrual if there is at least 90% probability that less than 75% of patients can continue to surgery without treatment-related delays, as shown in the following table:

#Patients planned for surgical resection	1	2	3	5	6	7	8
resection							
Out of total # evaluable patients	6	7	8-9	10	13	14-15	16

Exploratory analyses as detailed in the biomarker table/summary will be presented descriptively, and are detailed in the researcher comments section.

Sample Size Determination:

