12.1. Study Design

This is an open-label pilot study aimed at establishing the safety and feasibility of neoadjuvant immunoradiation prior to surgical resection of stage III NSCLC, that is deemed surgically resectable by a thoracic surgeon with lobectomy. Thoracic RT will be given at standard doses and fractionation to a total dose of 45Gy in 25 fractions, as per published phase III data⁴⁹, and using standard methods. In cohort 1, the safety and feasibility of durvalumab with concurrent thoracic RT, will be assessed. In this cohort, durvalumab will be administered at the standard dose of 1500mg IV every 4 weeks for 3 doses, as per ongoing phase III studies. If preliminary safety is established in cohort 1, the study will expand to include cohort 2, which will test the safety and feasibility of durvalumab plus tremelimumab with concurrent thoracic RT. In this cohort, durvalumab will be administered at the standard dose of 1500mg IV every 4 weeks for 3 doses, and tremelimumab will be administered at the standard dose of 75mg every 4 weeks for 3 doses. The primary endpoints of this study are safety and feasibility in cohort 1 and cohort 2 (if applicable). Patients will be observed for perioperative grade 3-4 adverse events through day 90 following the last dose of immunotherapy or until 30 days post-surgery, whichever is longer. Safety and feasibility will be monitored continuously throughout the study through weekly meetings with investigators, as well as the planned Bayesian monitoring rules (see below). A set of markers of immune reactivity measured in lung tumor resection specimens, draining lymph nodes, and peripheral blood will be evaluated. Feasibility will be evaluated as the proportion of evaluable patients who successfully complete preoperative treatment and proceed to surgery without any extended treatment related delays. Extended treatment-related delay will be defined as >8 weeks from the day of completion of thoracic RT. For each cohort, we aim to accrue 16 evaluable patients, defined as those who receive at least one dose of durvalumab or durvalumab/tremelimumab administration and have complete toxicity follow-up. We plan to accrue 20 patients to ensure 16 evaluable patients are available for analysis. If less than 16 evaluable patients are available after accruing 20 patients, we will amend the protocol to ensure at least 16 evaluable patients are available for analysis.

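### The feasibility pause rule has two conflicting cut-offs (90% in the synopsis, 70% in Section 12.2.3), and Table 10.6 does not describe Table 10.5: at 75% feasibility the printed rule pauses the study 36.8% of the time, not 6.4%

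*Combined protocol and SAP*

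**What the plan says.** The synopsis (Statistical methods) says the rule would "suspend the accrual if there is at least 90% probability that less than 75% of patients can continue to surgery without treatment-related delays". Its table, headed as patients planned for surgical resection, reads 1 of 6, 2 of 7, 3 of 8-9, 5 of 10, 6 of 13, 7 of 14-15 and 8 of 16.

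Section 12.2.3 calls the regimen infeasible if "the probability of not proceeding to surgery as planned is convincingly (more than 70%) more than .25". On the prior for the delay rate it says: "This corresponds to a Beta (0.1,0.9) prior distribution". Monitoring is continuous, "starting from the 6th evaluable patient", up to 16 evaluable patients per cohort. Table 10.5 sets the boundary at 3 delays of 6-7, 4 of 8-10, 5 of 11-14 and 6 of 15-16. On the consequence: "The feasibility stopping rule calls for the study to be paused for a review".

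Table 10.6 is offered as that rule's operating characteristics: "Table 10.6 summarizes the operating characteristics based on 5,000 simulations with 16 evaluable patients in terms of how frequent the study would stop". At feasibility 0.65, 0.70, 0.75 and 0.80 it gives stopping rates of 37.9%, 13.9%, 6.4% and 2.1%, and expected sample sizes of 13.8, 15.2, 15.6 and 15.9.

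Section 12.1 mentions only "as well as the planned Bayesian monitoring rules (see below"). It does not say which version governs.

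**The concern.** The two cut-offs give different decisions on the same data. If the synopsis row counts patients who reach surgery, 3 delays among the first 6 patients pause the study under Table 10.5 but not under the synopsis, which waits for 5.

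Table 10.6 also looks too favourable for a boundary as tight as 3 of 6. If its figures belong to another rule, the IRB and the safety board have been told that a regimen with 75% or 80% feasibility will almost never be paused. They have also been told that a poor regimen will be caught less often than the printed boundary would catch it. Crossing the boundary leads to a review and possible redesign of the regimen, so these figures bear on a real decision.

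**Working it through.** **Inputs.** All are from Section 12.2.3: looks at every evaluable patient from the 6th to the 16th, the Table 10.5 boundary, the Beta(0.1, 0.9) prior, the 0.25 delay limit and the 70% cut-off. The synopsis supplies the 90% cut-off and its own table.

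**Check of the method on the plan's own figures.** An exact forward recursion tracks the number of events patient by patient and removes the probability that reaches the boundary. Applied to the safety rule in Section 12.2.2 (Beta(0.05, 0.95), 25% limit, 70% cut-off, from the 3rd patient), it gives 16.3%, 29.3%, 44.3%, 59.4% and 72.8%. Table 10.2 prints 15.8%, 29.3%, 43.1%, 60% and 72.8%. The method reproduces that table to within 1.2 points.

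**A check by hand on Table 10.6.** At 75% feasibility the delay probability is 0.25. The first look alone pauses the study if at least 3 of 6 are delayed:

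1 − [0.75⁶ + 6(0.25)(0.75⁵) + 15(0.25²)(0.75⁴)] = 1 − (0.178 + 0.356 + 0.297) = 0.169.

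That one look gives 16.9%, already above the 6.4% stated for all eleven looks. At 80% feasibility it gives 1 − (0.262 + 0.393 + 0.246) = 9.9%, against 2.1% stated.

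**Full recursion for Table 10.5.**

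| True feasibility | Table 10.6, % stopped | Exact, % stopped | Ratio | Table 10.6, E[N] | Exact, E[N] |
|---|---|---|---|---|---|
| 0.65 | 37.9 | 67.7 | 1.8 | 13.8 | 10.6 |
| 0.70 | 13.9 | 52.8 | 3.8 | 15.2 | 11.9 |
| 0.75 | 6.4 | 36.8 | 5.7 | 15.6 | 13.1 |
| 0.80 | 2.1 | 21.8 | 10.4 | 15.9 | 14.3 |

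The standard error with 5,000 simulations is √[p(1−p)/5000], or 0.2 to 0.7 points over these values. The gaps are 20 to 39 points. A 200,000-run simulation gave 36.7% at 0.75. Other readings do not close the gap at 0.75: pausing only when the boundary is exceeded gives 15.6%, and a single look for 6 or more of 16 gives 19.0%.

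**Does Table 10.5 follow from its stated inputs?** After k delays in n patients the posterior is Beta(0.1 + k, 0.9 + n − k). The probability that the delay rate exceeds 0.25 is 0.705 at 3 of 8, 0.735 at 4 of 11 and 0.706 at 5 of 15. All exceed 70%, yet Table 10.5 asks for one more delay each time. Two settings reproduce Table 10.5 exactly: Beta(0.2, 1.8) with 70%, or the stated Beta(0.1, 0.9) with 75%.

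**The synopsis boundary.** Reading its top row as patients reaching surgery, delays at the boundary run from 5 of 6 to 8 of 16. The table has no entry for 11 or 12 patients, and its 10-patient cell is irregular. Over 18 ways of completing it (n = 10 at 5 or 6 delays; n = 11 and 12 at 6 or 7 delays or no look), it stops 23.4-30.6%, 12.7-18.4%, 5.7-9.4% and 2.0-3.8% of the time at the four feasibility values. Every version lies far below Table 10.5.

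**Possible origin of Table 10.6 (inference only).** With the synopsis gaps filled smoothly, its boundary gives 13.4%, 6.1% and 2.2% at 0.70, 0.75 and 0.80, with E[N] 15.2, 15.6 and 15.9, close to Table 10.6. The column labelled 0.65 matches only if the true value was 0.60 (38.3%, E[N] 13.7).

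**The case against.** Crossing the boundary triggers a review, not closure, and the final feasibility analysis is a proportion with an exact 95% interval that does not use Table 10.6. Table 10.5 is stricter than Table 10.6 implies, so following it gives no less monitoring. At the plan's own expected 10% delay rate it pauses only 3.3% of the time. The value 0.75 is itself the decision limit, so a pause there is not plainly an error. All of this stands and limits the harm, but it does not make Table 10.6 correct or settle which rule applies.

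The synopsis table may have lost columns in text extraction, and its heading has to be interpreted. The comparison of boundaries is therefore conditional. The 90% and 70% cut-offs are in running sentences and do not depend on it. The synopsis states no feasibility prior, so its boundary cannot be faulted against Beta(0.1, 0.9) as an internal error; the derivation fault is confined to Table 10.5. The account of where Table 10.6 came from is a guess that the conclusion does not need.

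**Conclusion.** The concern holds. Current text contains two cut-offs for one co-primary monitoring rule, with no order of precedence. Table 10.6 misstates the printed Table 10.5 boundary in every column: the pause probability is understated 1.8-fold at 0.65, 3.8-fold at 0.70, 5.7-fold at 0.75 and 10.4-fold at 0.80, and expected sample size is overstated by 1.6 to 3.3 patients. Table 10.5 also differs from its stated prior and cut-off at three sample sizes. The calculation assumes independent patients with a constant delay probability, a look at every patient from the 6th, and a pause on reaching the boundary. It must be fixed before the rule can be applied or its properties relied on.

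**What to change.** Choose one cut-off and one prior, derive the boundary from them, print the same rule and table in the synopsis and Section 12.2.3, and replace Table 10.6. The choice is the sponsor's. Consistent options, with values at feasibility 0.65 / 0.70 / 0.75 / 0.80:

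| Rule | Boundary (delays of patients) | % paused | E[N] |
|---|---|---|---|
| 70%, Beta(0.2, 1.8); or 75%, Beta(0.1, 0.9) | Table 10.5 as printed | 67.7 / 52.8 / 36.8 / 21.8 | 10.6 / 11.9 / 13.1 / 14.3 |
| 70%, Beta(0.1, 0.9) | 3 of 6-8, 4 of 9-11, 5 of 12-15, 6 of 16 | 73.4 / 59.4 / 43.3 / 27.1 | 10.0 / 11.3 / 12.6 / 13.9 |
| 90%, Beta(0.1, 0.9) or Beta(0.2, 1.8) | 4 of 6-7, 5 of 8-10, 6 of 11-13, 7 of 14-16 | 40.8 / 26.1 / 14.3 / 6.3 | 13.3 / 14.3 / 15.0 / 15.6 |
| 90%, Beta(0.5, 4.5) | 5 of 6-8, 6 of 9-11, 7 of 12-14, 8 of 15-16 | 24.4 / 13.4 / 6.1 / 2.2 | 14.6 / 15.2 / 15.6 / 15.9 |

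Beta(0.2, 1.8) keeps the stated 10% mean and roughly 14% prior probability above 0.25 (14.4%, against 14.2% for Beta(0.1, 0.9)). Beta(0.5, 4.5) lowers that probability to 11.7%, so the text would have to change.

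The cost is wording in two places and one recomputed table, with no new patients or data. The trade-off should be stated: keeping Table 10.5 or the 70% rule means accepting much higher pause rates at 0.75 and 0.80 than now printed, while a 90% rule detects 65% feasibility only 24-41% of the time, against 68-73%.

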12.3. Statistical Analysis Plan

12.3.1. Analysis Plan for Primary Endpoints

The proportion of adverse events of interest and feasibility will be reported along with the associated exact binomial 95% confidence intervals. Adverse events for each regimen will also be tabulated by type, grade, and attribution of adverse event.

12.3.2. Analysis Plan for Secondary Endpoints

Pathologic response will be stratified as showing MPR (>90% reduction in tumor cells), PR (10-90%) or NR (0-10%). The proportion of patient's whose tumor samples achieve MPR, PR and NR will be tabulated. The relationship between pathologic response in post-treatment resection specimens and clinical outcomes such as RFS, OS and surgical morbidity/mortality will be assessed through log-rank test and Cox proportional hazards (PH) model. Radiologic response will be evaluated by RECIST 1.1 and immunerelated RECIST criteria at time points specified in the Schedule of Assessments (Figure 1). The relationship between radiologic response in post immunoradiation CT scans and clinical outcomes including RFS, OS and surgical morbidity/mortality will be assessed using log-rank and Cox PH model. RFS will be defined as time from commencement of study therapy until the date of radiologic evidence of local or distant recurrent NSCLC. OS) will be defined as the time from commencement of protocol treatment until death due to any cause. RFS and OS will be calculated using the Kaplan-Meier method, and will be analyzed as time-to-event data. All adverse events that occur from the time of surgery until 30 days post-surgery or from the last dose of immunotherapy until 100 days, will be similarly summarized by type and grade. Any deaths that occur in this time period will be recorded. Attributions to the development of AEs or death in this time period will be recorded as either definitely related, possibly related, probably related or unrelated to study therapy.

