2.2. Secondary Objective(s)

- (1) Examine pathologic responses in post-treatment resection specimens, in patients with resectable stage III NSCLC treated with preoperative immunoradiation followed by surgery.
- (2) Examine radiologic responses in stage III resectable NSCLC treated with preoperative immunoradiation, using RECIST 1.1 and immune-related (ir) RECIST criteria
- (3) Evaluate recurrence-free survival (RFS) in patients with stage III resectable NSCLC treated with preoperative immunoradiation followed by surgery, where RFS is defined as the time from commencement of therapy until the development of local or distant recurrent disease.
- (4) Evaluate surgical morbidity and mortality in patients with stage III resectable NSCLC treated with preoperative immunoradiation followed by surgery, where morbidity is defined as the number treatment-related AEs, and mortality is the number of deaths, from the day of surgery until 30 days postoperatively or 100 days after the last dose of immunotherapy, whichever is longer.
- (5) Evaluate overall survival (OS) in patients with stage III resectable NSCLC treated with preoperative immunoradiation followed by surgery, where OS is defined as the time from commencement of therapy until death from any cause.

18 Nov 2020 Page **54** of **164**

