10.1.3. Surgical Morbidity and Mortality

[figure not shown]
Adverse events of any grade that occur in the postoperative period (day of surgery until 30 days post surgery), will be collected. These data will be obtained by weekly review of the subject's medical record by study investigators. The attributions of these AEs will also be recorded, as per section 9.3. Deaths that occur in the postoperative period will be recorded, and the attribution of any subject death will be recorded.

18-Nov-2020 Page **111** of **164**

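### Section 12.3.2 prescribes log-rank and Cox to relate response to surgical morbidity/mortality, which the protocol defines as counts in a perioperative window and never as a time-to-event endpoint

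*Combined protocol and SAP*

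**What the plan says.** Section 12.3.2 names one pair of methods for relating pathologic response to outcomes: "RFS, OS and surgical morbidity/mortality will be assessed through log-rank test and Cox proportional hazards (PH) model". It says the same for radiologic response: "RFS, OS and surgical morbidity/mortality will be assessed using log-rank and Cox PH model". The repetition makes a slip of the pen unlikely.

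The same section then defines RFS and OS, each with an origin (start of therapy) and an event, and adds: "RFS and OS will be calculated using the Kaplan-Meier method, and will be analyzed as time-to-event data". Surgical morbidity and mortality are not included in that sentence.

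Their definition is in section 2.2: "morbidity is defined as the number treatment-related AEs, and mortality is the number of deaths, from the day of surgery until 30 days postoperatively". The window there runs "until 30 days postoperatively or 100 days after the last dose of immunotherapy, whichever is longer". Section 10.1.3 uses a different window and a wider set of events: "Adverse events of any grade that occur in the postoperative period (day of surgery until 30 days post surgery), will be collected".

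Section 12.3.2 also gives a descriptive analysis. Adverse events after surgery "will be similarly summarized by type and grade", and deaths in the period are recorded with their attribution.

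**The concern.** Log-rank and Cox need an origin, an event time for each patient and a censoring rule. For surgical morbidity and mortality the documents give a number of events in a window. They do not say whether the event would be the first complication, the worst complication or death. Nor do they say when a patient without an event is censored.

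The analyst would have to construct the endpoint after seeing the data. Even the origin is open. The only origin named in 12.3.2 is the start of therapy, and a postoperative event cannot occur before surgery, so that choice would mix waiting time to surgery into the comparison. Section 2.2 opens its window on the day of surgery instead.

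What is at stake is one secondary association: whether response is related to surgical complications or death. For death there is also a data problem, because so few events are expected that a Cox hazard ratio would usually not exist.

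**Working it through.** The plan gives no sample size, effect size or error rate for this association, so there is no stated figure to reproduce.

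**Inputs from the documents**
- 16 evaluable patients per cohort (section 12.1).
- Perioperative mortality of about 4% (section 3.1.6.2). Section 1.6.5 also gives 0.5% for the single death after lobectomy in a phase III trial. That is a share of the whole arm: 16 deaths are 7.9% there, so the arm had about 16/0.079 = 203 patients, and 1/203 = 0.5%.
- About 50% major pathologic response (MPR) anticipated (section 10.2.1). Section 1.7.2 gives roughly 50/15/35% for MPR, partial response (PR) and no response (NR).
- Last dose on day 60, surgery 6 to 8 weeks after radiation (section 6.2.1).

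**Assumptions**: an 8/8 split by MPR; complication risks of 20% and 40%; radiation ending on day 33 to 35 (25 fractions, five per week).

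**Step 1. Endpoint against method**

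| Outcome | Origin | Event | Declared time-to-event | Method in 12.3.2 |
|---|---|---|---|---|
| RFS | start of therapy | recurrence | yes | log-rank, Cox |
| OS | start of therapy | death | yes | log-rank, Cox |
| Surgical morbidity | none for an event time | number of AEs | no | log-rank, Cox |
| Surgical mortality | none for an event time | number of deaths | no | log-rank, Cox |

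**Step 2. Expected deaths**
- n = 16, 4%: 16 × 0.04 = 0.64. P(none) = 0.96^16 = 52%. P(at most one) = 87%.
- n = 16, 0.5%: 16 × 0.005 = 0.08. P(none) = 0.995^16 = 92%.
- n = 32, if both cohorts were pooled, 4%: 1.28 expected. P(none) = 0.96^32 = 27%.

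**Step 3. Chance that at least one response group has no events**, 1 − (1 − q)², where q = (1 − p)^8:
- p = 4%: q = 0.721, result 92%. This includes the 52% with no deaths at all (hazard ratio undefined); the other 40% give a ratio of zero or infinity.
- p = 20%: q = 0.168, result 31%.
- p = 40%: q = 0.017, result 3%.

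Pooling to 16/16 at 4% still gives 1 − (1 − 0.520)² = 77%. With three categories at about 8/2/6 (50/15/35% of 16, rounded), the chance that at least one is empty of events is 1 − (1 − 0.96^8)(1 − 0.96^2)(1 − 0.96^6) = 99.5% at 4%, 78% at 20% and 40% at 40%.

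**Step 4. Whether the choice of method matters.** Take 4/8 against 1/8 patients with an event, followed to day 30. If the four events fall on days 1–4 and the other on day 29, log-rank p = 0.085. If they fall on days 26–29 and the other on day 1, p = 0.154. Fisher's exact test gives p = 0.28 in both cases.

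**Step 5. Error rates.** In 3,000 simulated null trials (8/8, uniform event times over 30 days, nominal 5%):
- 20% risk: log-rank rejects in 2.2%, Fisher in 0.5%.
- 40% risk: log-rank rejects in 5.8%, Fisher in 2.2%. The simulation standard error for 5.8% is √(0.058 × 0.942/3000) = 0.4 points.

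**Step 6. Window.** Surgery falls between day 33 + 42 = 75 and day 35 + 56 = 91. One hundred days after day 60 is day 160. The section 2.2 window therefore lasts 160 − 91 = 69 to 160 − 75 = 85 days after surgery and varies by patient, against a flat 30 days in section 10.1.3. Section 12.3.2 lists the two periods without saying that the longer one applies, and starts the 100-day period at the last dose, which precedes surgery.

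**The case against.** There are four good points on the plan's side.

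- **These events are analysed elsewhere.** A reader might infer that surgical morbidity and mortality get no suitable analysis at all. The documents do not support that. Section 12.3.2 tabulates the events by type and grade and records deaths and attribution, and section 12.3.1 gives exact binomial intervals for the primary endpoints. Only the association with response is affected.
- **Event dates exist.** Section 9.3 collects start and stop dates of adverse events and, for serious events, the date of death. Time from surgery to first event could be derived. This stands: the missing parts are the event definition, the origin for analysis and the censoring rule. Defining such an endpoint would be a legitimate alternative repair.
- **Sparsity is shown for death only.** A reader might infer that Cox would also break down for morbidity. The 4% figure concerns death and says nothing about complications. With an 8/8 split, the chance of an event-free group falls to 31% at a 20% risk and 3% at 40%. A group with no events also makes an odds ratio zero or infinite, so sparsity alone does not argue against Cox.
- **Log-rank is not shown to mislead.** A reader might infer inflated false-positive rates. The simulated 2.2% and 5.8% show no serious inflation, and Fisher's test is clearly more conservative.

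It would also be too strong to call the outcome yes/no in a fixed window. Section 2.2 defines morbidity as a count, and its window differs between patients.

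None of this supplies a time-to-event definition for surgical morbidity or mortality, so the mismatch remains.

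**Conclusion.** The point holds, narrowly. Section 12.3.2 twice assigns time-to-event methods to an outcome that section 2.2 defines as numbers of events and that no section turns into a time-to-event endpoint.

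For mortality the prescribed Cox analysis would usually yield no usable hazard ratio: 0.64 expected deaths and about a 92% chance of an event-free group. This rests on the 4% reference rate, 16 patients and the assumed 8/8 split. Sixteen is generous, because section 12.1 counts a patient as evaluable after one dose with complete toxicity follow-up, whereas pathologic response exists only in patients who had surgery.

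For morbidity the defect is the mismatch itself. How sparse the data would be depends on a complication rate that the documents do not give.

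The point is minor: a secondary, exploratory association in a pilot study. The primary safety and feasibility analyses and the descriptive tabulation stand as they are.

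**What to change.** 1. In section 12.3.2, restrict log-rank and Cox to RFS and OS, in both the pathologic and the radiologic sentence.
2. Reconcile the windows in sections 2.2, 10.1.3 and 12.3.2 into one, opening at surgery. State whether morbidity means treatment-related events (2.2) or all events (10.1.3); the indicator below follows 2.2.
3. Define two per-patient indicators among operated patients: any treatment-related postoperative adverse event, and death, within that window.
4. Report each proportion by response category (MPR/PR/NR, and radiologic category) with exact 95% confidence intervals. Compare with Fisher's exact test, or its Fisher-Freeman-Halton extension for three groups, labelled descriptive.

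If a time-to-event analysis is truly wanted, the plan should instead define the origin, the qualifying event and the censoring rule.

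The cost is a few sentences in three sections and no new data. The price is low power. With 8 against 8, Fisher's test reaches two-sided p < 0.05 only from five events in one group and none in the other (5 v 0: p = 0.026; 4 v 0: p = 0.077). Its null rejection rate was 0.5% to 2.2% in step 5. Mortality can therefore only be described. With no deaths among 8 patients, the exact upper 95% limit is 1 − 0.025^(1/8) = 37%, which shows the reader how little the comparison can say.
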